16.2. Analysis of outcomes

A separate Statistical Analysis Plan will be produced and will provide a more comprehensive description of the planned statistical analyses. A brief outline of the planned analyses is given below.

Unless reported otherwise, the threshold for determining statistical significance from hypothesis testing will be represented by a p-value of <0.05. Where parametric tests have been specified dependent on the normality of data distribution, this will be assessed using appropriate graphics (for example histograms and q-q plots) prior to application of the test. Where randomisation is minimised by stratification variables, the main estimators will be adjusted for such variables for the primary outcome at stage R1.

Data pertaining to outcome measures will be transformed as per user manuals and standard practice to derive clinically meaningful indices where relevant.

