6.5.1. Randomisation method

Participants will be randomised at the level of the individual in a 1:1 ratio to either Tirzepatide or standard of care. The randomisation process for initial randomisation R1 will use a minimisation algorithm to ensure balance in the treatment allocation for the following variables:

- Baseline acetazolamide status (currently taking, yes/no)

To avoid the possibility of the intervention allocation becoming predictable, a random element will be included in the algorithm. Full details of the randomisation specification will be stored in a confidential document at BCTU.

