8.1.2. Secondary outcomes

All secondary outcomes measured at 6 months post-randomisation unless stated otherwise:

- Clinical outcomes:
 - Change in papilloedema as measured by OCT
 - Headache: Monthly headache days (MHD), Monthly migraine days, Headache responder rate ($\geq 50\%$ reduction in MHD), Monthly analgesic days and Monthly headache severity (numerical rating scale lowest 0-10 highest).
 - Headache disability (using the Headache Impact Test-6 (HIT-6))

- Weight and BMI
- Patient-centred outcomes:
 - Quality of Life (QoL) measured using the 36-item short form survey (SF-36) summary score, physical component score and mental component score
 - QoL measured using the EQ-5D-5L
 - Vision related QoL measured using the National Eye Institute Visual Function Questionnaire-25 (NEI-VFQ-25) plus the 10-item supplement
 - Binge eating measured using the Binge Eating Scale (BES)
 - Alcohol use measured using the Alcohol Use Disorders Identification Test (AUDIT)
 - Anxiety and depression measured using the Hospital Anxiety and Depression Scale (HADS)
 - Tolerability of weight loss in IIH driven by Tirzepatide as determined by all cause discontinuation at 6, 12 and 18 months
- Service use outcomes:
 - Service use (doctor attendance, hospital attendance, days in hospital, lumbar punctures, brain imaging scans) (as recorded by Client Service Receipt Inventory (CSRI))
 - Medication use (use and dose of acetazolamide or other ICP lowering drugs)
 - Absenteeism and presenteeism measured using the Work Productivity and Activity Impairment (WPAI) Scale

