16.2.2. Secondary outcomes

Binary outcomes will be compared using an analogous method to that described under the primary outcome.

Non-ophthalmologic continuous, or pseudo-continuous outcomes collected only once post-baseline will be displayed as change from baseline and will be analysed using a linear regression model adjusted for baseline where appropriate. Results will be presented as adjusted mean differences with 95% confidence intervals. Statistical significance of a difference between treatment arms will be assessed based on the model.

Non-ophthalmologic continuous, or pseudo-continuous outcomes where the outcome is collected at multiple timepoints post-baseline (including patient reported outcome measures) will be assessed for differences between arms using mixed effect repeated measures models using linear patient trajectories through time (alternative analytical functions of time may be considered as necessary). In the initial model, a treatment by time interaction effect will be included in the model. If this is not significant, it will be considered that the treatment effect is constant over time, and models without the treatment by time interaction term will be fitted. Results will be presented as adjusted mean differences and 95% confidence intervals.

Ophthalmologic continuous, or pseudo-continuous outcomes (OCT outcomes) may have data collected in more than one eye. To best use this and increase statistical efficiency while accounting for the non-independence and high correlation between eyes within individuals, we will use hierarchical models to nest observations within patients. These models will have adjustments for treatment allocation and group-level effects for the effect of eye within participant. The presence of a linear predictor and slope-varying terms will be dependent on the number of post-baseline observations. The presence of a treatment effects will also be tested by a likelihood ratio test against a nested model with no treatment variable and otherwise identical model specification.

Ordinal outcomes will be analysed akin to the continuous outcomes however will be compared between treatment arms using ordered logistic regression models.

Data pertaining to exploratory outcomes will be summarised descriptively and/or graphically using methods appropriate to the data type. Exploratory outcomes will be presented separately for each of the (randomisation) questions (R2a, R2b, R2c, SA3a, SA3b).

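### The protocol states adjustment for the minimisation factor only for the primary outcome; omitting it for 6-month acetazolamide use would give intervals that are too wide and a conservative test

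*Protocol*

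**What the plan says.** Section 6.5.1 lists a single minimisation variable for R1, "Baseline acetazolamide status (currently taking, yes/no"), and adds that "a random element will be included in the algorithm"; the probability is not given. Section 16.2 then sets the scope of covariate adjustment: "the main estimators will be adjusted for such variables for the primary outcome at stage R1".

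Section 8.1.2 includes among the 6-month secondary outcomes "Medication use (use and dose of acetazolamide or other ICP lowering drugs").

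Section 16.2.2 describes the secondary models:
- Binary: "Binary outcomes will be compared using an analogous method to that described under the primary outcome". Section 16.2.1, to which this points, gives logistic regression with marginal standardisation and names no covariate.
- Continuous, one post-baseline measurement: "will be analysed using a linear regression model adjusted for baseline where appropriate".
- Continuous, repeated: "mixed effect repeated measures models using linear patient trajectories through time", with no baseline covariate named, although the results are called adjusted.
- OCT: "These models will have adjustments for treatment allocation and group-level effects for the effect of eye within participant". The minimisation factor is not in that list.

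Sections 16.2.1 and 16.2.4 count a missing primary outcome as a failure, and section 16.2.4 extends an analogous strategy to binary secondary outcomes. Section 16.1 plans for 25% attrition.

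**The concern.** Minimisation makes the arms nearly equal on acetazolamide status, so chance imbalance in that factor hardly contributes to the real sampling variation of a treatment comparison. A model without the factor leaves the factor's whole contribution in the residual variance and reports a standard error as if allocation had been simple. The overstatement grows with the factor's prognostic strength.

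For most secondary outcomes that strength is unknown and may be small. For acetazolamide use at 6 months, the factor is the outcome's own baseline value and is likely to be the strongest predictor available. What is at stake is a drug-sparing effect that could be missed, and an interval whose coverage is above its nominal 95%. The primary analysis is not touched, because there the adjustment is stated.

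**Working it through.** **Plan's own figure.** With 5% against 37%, two-sided alpha 0.05, power 90% and pooled proportion 0.21:

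n = [1.96·√(2·0.21·0.79) + 1.2816·√(0.05·0.95 + 0.37·0.63)]² / 0.32² = (1.129 + 0.679)² / 0.1024 ≈ 31.9, so 32 per arm. Then 32/0.75 = 42.7, so 43 per arm and 86 in all. This reproduces section 16.1 and is unaffected by the point. N = 86 is used below.

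**Inputs.** From the protocol: N = 86, 1:1 allocation, one binary minimisation factor, a random element, 25% attrition, missing counted as failure. Assumed, because the protocol gives no figures: 50% on acetazolamide at baseline; 6-month use of 90%/5%, 80%/10% or 70%/15% in baseline users/non-users; probability 0.8 of allocation to the under-represented arm.

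**By hand, no treatment effect, exact balance.** Let p̄ be overall use and w the mean within-status variance.
- Unadjusted model SE ≈ √(4·p̄(1−p̄)/N)
- True SD ≈ √(4·w/N)
- Overstatement ≈ √(p̄(1−p̄)/w)

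For 90%/5%: p̄ = 0.475 and p̄(1−p̄) = 0.2494; w = 0.5·0.09 + 0.5·0.0475 = 0.0688. The SE is 0.108 against a true SD of 0.057, a ratio of 1.90. For 80%/10%: √(0.2475/0.125) = 1.41. For 70%/15%: √(0.2444/0.1688) = 1.20. Exact balance is the limiting case; the random element brings the ratios down a little.

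**With 25% missing.** The protocol does not say whether failure means use or non-use here. Coded as non-use, 90%/5% becomes 67.5%/3.75%, with p̄(1−p̄) = 0.2293, w = 0.1277 and ratio 1.34. Coded as use, it becomes 92.5%/28.75%, with ratio √(0.2387/0.1371) = 1.32. Missingness unrelated to status dilutes the factor under either coding.

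**Simulation, 4,000 trials per scenario, no effect.** Unadjusted risk difference; the linear status-adjusted analysis with robust SE kept its size at about 5–6%.

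| Use at 6 months, users/non-users | SE ratio, complete | Test size, complete | SE ratio, 25% missing | Test size, 25% missing |
|---|---|---|---|---|
| 90%/5% | about 1.8 | about 0.1% | about 1.3 | 1–2% |
| 80%/10% | about 1.4 | about 1% | about 1.2 | 2–3% |
| 70%/15% | about 1.2 | about 3% | about 1.1 | 3–4% |

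**Power, starter rate equal in both arms, unadjusted then adjusted.**

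| Use at 6 months in baseline users, control vs Tirzepatide | Complete data | 25% missing |
|---|---|---|
| 90% vs 60% (5% starters) | 25–27%, then 55–57% | 17–18%, then 24–30% |
| 80% vs 50% (10% starters) | 28–30%, then 43–44% | 17–21%, then 20–28% |
| 70% vs 45% (15% starters) | 22–23%, then 27–29% | 14–18%, then 15–21% |

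Ranges reflect repeated runs and, for missing data, both codings of failure.

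**Same question by the protocol's own method** (logistic regression with marginal standardisation, complete data, 30–50% baseline users, starters also reduced on Tirzepatide). Leaving out status made the model SE 1.08 times the adjusted one at 60%/20% control-arm use, 1.19–1.20 times at 70%/10% and 1.49–1.53 times at 90%/5%. In the strongest case, across sample sizes of 64 and 86, 12–31% of simulated data sets were dropped for separation, so those figures are approximate.

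**Dose** (assumed mean 1000 mg, SD 350 mg at baseline among users, for arithmetic only; N = 86). With baseline dose in the model the SE is 60–84 mg; adding status leaves it at 60–84 mg, because a dose of zero already carries the status. With no baseline term, the SE is 87–115 mg for follow-up dose (1.25–1.63 times) and 68–102 mg for a plain change score (1.09–1.27 times).

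**The case against.** The strongest reply is that the analogous method for binary outcomes brings the covariate with it. The primary analysis is adjusted, and marginal standardisation does nothing without covariates, since it would return the raw proportions. That reading is natural, and omission for binary outcomes is therefore not certain. But the method it points to names no covariate, and the one sentence that does supply the adjustment confines it to the primary outcome. The two places need reconciling on either reading.

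A second reply is that covariate lists belong in the separate SAP, since section 16.2 calls itself a brief outline. That would answer silence. Here the protocol states a scope, and the OCT paragraph lists its adjustments without the factor.

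Three stronger inferences should be resisted. A reader might infer that acetazolamide dose also gets intervals that are too wide; under the baseline-adjusted linear model already named, it does not. The loss returns only if dose goes through the repeated-measures paragraph without a baseline term (concomitant medication is recorded monthly), or if the baseline adjustment is judged not appropriate. A reader might take the 1.8-fold figure as the expected size; that needs complete data and a very strong link. And a reader might suspect a false-positive risk; the error runs the other way.

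It also stands that section 16.1 powers only the primary R1 question, and that the outcome covers other pressure-lowering drugs, which acetazolamide status predicts less well.

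**Conclusion.** The point holds in a limited form. As written, the protocol commits to adjusting for its only minimisation factor for the primary outcome and leaves it unclear or absent elsewhere in R1. For binary acetazolamide use, an analysis without the factor overstates the standard error by about 1.2–1.8 times with complete data, and by about 1.1–1.3 times at the planned 25% missing. The power forgone is about 6–30 points and 0–13 points respectively. Missingness below 25% falls between.

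These sizes rest on assumed usage rates, an assumed 0.8 allocation probability and missingness unrelated to status. For the repeated-measures and OCT models the mismatch is in the text, but its size was not calculated. Estimates stay unbiased and type I error is not inflated. This is lost precision on unpowered secondary outcomes, worth correcting because the correction costs almost nothing.

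**What to change.** Replace the adjustment sentence in section 16.2 with:

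*All R1 treatment comparisons, primary and secondary (binary, continuous, repeated-measures, OCT and ordinal), will be adjusted for baseline acetazolamide status, and for the baseline value of the outcome where one is recorded.*

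This settles the binary case, adds the factor to the OCT and repeated-measures models, and secures baseline dose for the dose outcome whichever paragraph governs it.

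The cost is about one degree of freedom per model for the factor, with no new data or participants. Some logistic models may meet sparse cells or separation when few baseline non-users start the drug, so the SAP should name a fallback in advance, such as penalised logistic regression or a linear model with robust standard errors.

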16.2.1. Primary outcome

Resolution of papilloedema at the 6 month assessment. Where patients are missing the primary outcome (for example due to non-attendance at 6-month visit), they shall be treated as a failure and included in the denominator only (unless there is data from an unscheduled visits which could be utilised).

Resolution of papilloedema will be reported as n/N where n is the number of participants with resolution of papilloedema and N the total number of participants in the corresponding trial arm, and percentages as appropriate. Logistic regression model will be used to analyse the primary outcome. Risk ratio, risk difference and the associated 95% confidence intervals will then be derived using marginal standardisation method.

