16.1. Sample size

Examination of various IIH datasets held (including the IIH:WT trial²⁵, the IIH:Life cohort, and our previously published clinical trials in IIH²⁶) suggest it is anticipated that in the population of patients who receive standard of care only 5% will have resolution of papilloedema (100% reduction in the excess elevation of the optic nerve swelling). Further analysis of these datasets revealed that in those who achieved at least a 12% reduction in body weight, between 30 and 50% had a complete resolution of papilloedema. For the purposes of the sample size calculation, we have taken a conservative estimate of 37% (the median estimate).

With a type I error of 0.05, a type II error of 0.1 (corresponding to a power of 90%), a responder rate in the control arm of 5% and responder rate of 37% in the Tirzepatide arm, a sample size of 32 participants per arm is required. Inflating this to account for 25% attrition (for missing data and withdrawal) would require 43 patients per arm (86 overall).

After 50% of the planned sample size has been recruited and treated (i.e. at the end of the first randomisation R1), an assessment of the missing data is planned to ensure the levels observed fall below that assumed during this calculation, with the option to increase the sample size based on this if needed. This trial has been powered to answer the primary question for R1 only. The subsequent questions remain unpowered. This remains a limitation, however powering for these questions would result in a trial sample size that was infeasible. The purpose of these questions is to provide some high-quality evidence.

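### The primary analysis names a risk ratio and a risk difference with no lead measure or test; at the planned 5% control rate the risk ratio cannot be estimated in about 11-19% of trials

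*Protocol*

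**What the plan says.** Section 16.2.1 of the Protocol states that "Logistic regression model will be used to analyse the primary outcome", followed by "Risk ratio, risk difference and the associated 95% confidence intervals will then be derived using marginal standardisation method". Both measures are listed without ranking, and the section names no significance test. Section 16.2 sets a p-value threshold of 0.05 and adjusts the primary estimators for the minimisation variable, which section 6.5.1 gives as baseline acetazolamide use (yes/no). Sections 16.2.1 and 16.2.4 count missing primary outcomes as failures, apart from any rescued by an unscheduled visit.

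The planning figures are in section 16.1. It anticipates that "in the population of patients who receive standard of care only 5% will have resolution of papilloedema", and it uses "a responder rate in the control arm of 5% and responder rate of 37% in the Tirzepatide arm". From these, "a sample size of 32 participants per arm is required", raised to 43 per arm for 25% attrition.

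Section 16.2.2 does name a likelihood-ratio test for the OCT secondary outcomes, and it carries the primary method over to binary secondary outcomes. Section 16.2 describes its analysis text as an outline, with detail to follow in a separate SAP.

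**The concern.** By its own figures the plan expects 43 × 0.05 = 2.15 control responders, or 43 × 0.0375 = 1.6 if a quarter are missing and scored as failures. A ratio measure and a default Wald test behave poorly with so few events, and at zero they break down. The risk difference does not. A plan that lists both measures, ranks neither and names no test therefore leaves the primary conclusion dependent on which output is read. The trial is unblinded (section 6.6), so that choice should not remain open until the results are known.

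**Working it through.** **Inputs.** Response 5% vs 37%, alpha 0.05, power 90%, 32 evaluable and 43 randomised per arm, 25% attrition (section 16.1); missing counted as failure (16.2.1, 16.2.4). Sidedness is not stated; two-sided is assumed.

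**1. The plan's sample size.** Two-proportion formula with pooled null variance and no continuity correction:

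n = [1.960 × √(2 × 0.21 × 0.79) + 1.282 × √(0.05 × 0.95 + 0.37 × 0.63)]² / 0.32² = (1.129 + 0.679)² / 0.1024 ≈ 31.9, so 32. Then 32 / 0.75 = 42.7, so 43.

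The stated figures reproduce. A one-sided test with continuity correction also gives 32; two-sided with correction gives 38. Either way the basis is a chi-squared-type comparison of proportions.

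**2. Chance of no control responder,** (1 − p)^n:
- 43 analysed, none missing: 0.95^43 = 11.0% (1 in 9).
- 43 analysed, 25% missing as failures: (1 − 0.05 × 0.75)^43 = 0.9625^43 = 19.3% (1 in 5).
- 32 evaluable: 0.95^32 = 19.4%.

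This depends on the true control rate. At 3% the first two figures become 27% and 38%; at 8% they become 2.8% and 7.0%.

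**3. What happens then.** Logistic models with treatment and a binary covariate were fitted to illustrative data with 0/43 control responders. The 50% covariate split and the tirzepatide counts are assumptions.
- With 12/43 on tirzepatide, the treatment coefficient diverges (about 23 or over 1,000, depending on the software's stopping rule). The Wald p is about 1, and the risk ratio is infinite or arbitrary (above 10^9) with no usable interval.
- The standardised risk difference is finite: 0.28 (95% CI 0.15 to 0.41). With 16/43 it is 0.37 (0.23 to 0.52).
- The likelihood-ratio test gives p = 1.6 × 10^-5 and 3.6 × 10^-7.
- A Firth-penalised fit for 12/43 gives a risk difference of 0.28 (0.14 to 0.42) and a risk ratio of 24 (1.5 to 380).

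**4. Power by choice of test.** Exact enumeration of both binomial counts, without covariate, two-sided 5%. Trials in which a Wald ratio test cannot be computed count as not significant. In the third row, 3.75% and 27.75% are 0.75 times the planned rates.

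| Scenario | Wald, log odds ratio | Wald, log risk ratio | Risk-difference CI excludes 0 | Chi-squared | Risk ratio and risk difference disagree |
|---|---|---|---|---|---|
| 32 per arm, 5% vs 37% | 71.3% | 69.5% | 94.1% | 92.8% | 24.6% |
| 43 per arm, 5% vs 37% | 86.3% | 85.8% | 98.0% | 98.0% | 12.3% |
| 43 per arm, 3.75% vs 27.75% | 68.8% | 67.2% | 92.0% | 92.0% | 24.9% |

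The first and third rows correspond to the planned 90% power. Every disagreement is a significant risk difference with a risk ratio that is non-significant or not estimable. Most come from zero-responder trials: 19.4 of the 24.6 points, 11.0 of 12.3 and 19.3 of 24.9. Coverage of the risk-difference interval is 94.3%, 94.1% and 93.9%.

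**5. Type I error.** The same enumeration with equal rates in both arms (32 per arm at 5%; 43 per arm at 5% and 3.75%) gives rejection rates of 3.2-4.7% for the risk difference and chi-squared tests, but 8.6-9.1% for the unpenalised likelihood-ratio test.

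**The case against.** Two stronger readings are tempting, and the document supports neither.

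A reader might infer that the primary model cannot be fitted when no control participant responds. It can: the fitted control probability goes to zero, and the standardised risk difference and its delta-method interval remain finite (step 3). That interval gives the control arm essentially no variance, which is an imperfection, but its coverage over all trials is about 94%.

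A reader might also infer that the trial has only about 70% power. That would require significance to be read from a Wald test on a ratio scale, and the Protocol never says so; the odds ratio is not even a reported measure. Read from the risk difference, the plan delivers its 90% and agrees with the basis of the sample size. With no control responders the treatment conclusion is not itself in danger, because the risk difference clearly excludes zero in the illustrations.

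It is also fair to say that handling of separation, interval method and choice of test are commonly left to an SAP, and that logistic regression with marginal standardisation is a recognised approach. The absence of a sparse-data fallback alone would not be a finding. What stands is what the Protocol does fix: two unranked primary measures, one of which its own 5% assumption makes inestimable in a material share of trials, with no test to settle which one decides.

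**Conclusion.** The point holds as a should-fix. Under the Protocol's planning figures the risk ratio, its interval and a Wald p-value for treatment are unavailable in about 11% of trials (43 analysed) to 19% (25% missing as failures). In the 90%-power scenarios the choice of scale moves power between 67-71% and 92-94%. Across the planning scenarios the two named measures disagree on significance in about 12-25% of trials.

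These figures rest on a true control rate near 5%, on equal attrition in the arms that is unrelated to response, on unadjusted enumeration, on a risk-ratio interval built on the log scale, and on counting an inestimable risk ratio as non-significant. A control rate of 8% would shrink the zero-responder problem to 3-7% of trials. The unseen SAP may already resolve part of it.

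**What to change.** In section 16.2.1, or in the SAP before any outcome data are compared by arm:

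- Name the standardised risk difference, with its 95% interval, as the lead primary measure.
- Take the primary p-value from an acetazolamide-stratified score (CMH) test or a likelihood-ratio test, not a Wald test. Of the two, the score test is preferable: with so few events the unpenalised likelihood-ratio test rejected in about 9% of null trials in step 5, whereas the unstratified score test stayed below 5%.
- Report the risk ratio as supportive. State that a Firth-penalised fit or a score interval will be used when an arm has zero or very few responders.
- Apply the same rule to the binary secondary outcomes, which inherit the primary method.

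The cost is a few lines of analysis wording and standard software, with slight shrinkage where the penalised fit is used. Design, data collection and sample size do not change.
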